Pregnancies occurring while the subject is on study drug or within 4 weeks after the subject's last dose of study drug are considered immediately reportable events. If the subject is on study drug the study drug is to be discontinued immediately and the subject is to be instructed to return any unused portion of the study drug to the Investigator. The pregnancy must be reported to the Safety Monitor within 24 hours of the Investigator's knowledge of the pregnancy by phone and facsimile using the SAE Form.

Protocol Version Date: November 25, 2014

The Investigator will follow the subject until completion of the pregnancy, and must notify the Safety Monitor of the outcome within 5 days or as specified below. The Investigator will provide this information as a follow-up to the initial SAE.

If the outcome of the pregnancy meets the criteria for immediate classification as a SAE (i.e., spontaneous abortion [any congenital anomaly detected in an aborted fetus is to be documented], stillbirth, neonatal death, or congenital anomaly), the Investigator should follow the procedures for reporting SAEs (i.e., report the event to the Safety Monitor by telephone and facsimile within 24 hours of the Investigator's knowledge of the event).

All neonatal deaths that occur within 30 days of birth should be reported, without regard to causality, as SAEs. In addition, any infant death after 30 days that the Investigator suspects is related to the *in utero* exposure to the study drug should also be reported.

In the case of a live "normal" birth, the Safety Monitor should be advised as soon as the information is available.

10.6 **Required Routine Reporting**

Adverse events to be graded at each evaluation and pretreatment symptoms/conditions to be evaluated at baseline per the CTCAE v4.0 grading unless otherwise stated in the table below:

| System Organ Class (SOC) | Adverse event/Symptoms | Baseline | Each evaluation |
|--------------------------------------|---------------------------|----------|--------------------|
| Investigations | Platelet count decreased* | X | Х |
| Blood and lymphatic system disorders | Anemia* | X | Х |
| Gastrointestinal disorders | Constipation | Х | Х |
| | Ileus | | Х |

* Grading will be performed by the study statisticians at the time of analysis based on the CLL toxicity grading scale for blood counts in Appendix V. Anemia grade per CTCAE will also be recorded for reporting purposes.

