- 10.61 Submit via appropriate MCCC Case Report Forms (i.e., paper or electronic, as applicable) the following AEs experienced by a patient and not specified in Section 10.6:
 - 10.611 Grade 2 AEs deemed *possibly*, *probably*, *or definitely* related to the study treatment or procedure.
 - 10.612 Grade 3 and 4 AEs regardless of attribution to the study treatment or procedure.
 - 10.613 Grade 5 AEs (Deaths)

Protocol Version Date: November 25, 2014

- 10.6131 Any death within 30 days of the patient's last study treatment or procedure regardless of attribution to the study treatment or procedure.
- 10.6132 Any death more than 30 days after the patient's last study treatment or procedure that is felt to be at least possibly treatment related must also be submitted as a Grade 5 AE, with a CTCAE type and attribution assigned.
- 10.62 Refer to the instructions in the Forms Packet (or electronic data entry screens, as applicable) regarding the submission of late occurring AEs following completion of the Active Monitoring Phase (i.e., compliance with Test Schedule in Section 4.0).

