- 15.26 **Potential Drug Interactions**: The results of studies to date show no inhibition or induction of activities for any CYP isoform tested. In induction studies, slight decreases in activities of CYP2B6, 3A4, CYP2C9 and UDPGT were actually observed, which were again considered to be a non-specific effect on these enzymes. Overall, data suggest negligible to minimal effects of AT-101 on CYP450 enzyme activities at concentrations likely to be achieved in humans.
- 15.27 **Known potential toxicities**: The most frequent adverse events associated with AT-101 dosing have been gastrointestinal findings such as nausea and vomiting; anorexia, dehydration, hypokalemia and fatigue have also been frequent. Most adverse events have been of low grade (Grade 1-2 on the NCI Common Toxicity Criteria scale), but a clinical picture of ileus/nonmechanical small bowel

obstruction has also been observed in approximately 10-15% of patients receiving 30 mg of AT-101 daily or daily for 21 of 28 days. Following these initial observations the dosing schedule of single-agent AT-101 was modified and the dose reduced for continuous dosing schedules over multiple cycles (from 30 mg/day to 20 mg/day for 21/28 days). The incidence of ileus/non-mechanical small bowel obstruction was reduced to approximately 5%. Please review the Investigator's Brochure for more detailed information regarding ileus/non mechanical small bowel obstruction.

15.28 **Drug procurement:** AT-101 will be provided free of charge to patients by Ascenta Therapeutics.

15.29 Nursing Guidelines:

- 15.291 AT-101 should be taken on an empty stomach (at least one hour before or after meals).
- 15.292 GI side effects were the most common. Nausea, vomiting, anorexia were the most common. Treat symptomatically and monitor for effectiveness.
- 15.293 Monitor electrolyte levels, hypokalemia is common.
- 15.294 Fatigue has been seen. Instruct patient on energy conserving lifestyle and monitor for effectiveness.
- 15.295 Monitor bowel function. Patients getting higher and prolonged doses of the agent have presented with higher (10-15% vs. 5%) rates of ileus/or mechanical small bowel obstruction.

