- 16.225 Dose de-escalation: If dose-limiting toxicity meets the stopping boundaries set by the above dose escalation algorithm at dose level 1 (for example, more than 1 out of 3 patients or more than 1 out of 6 patients), the next cohort of three patients will be entered at a dose level of -1. If dose level -1 meets the stopping boundaries, the next cohort of three patients will be entered at dose level -2. Further dose re-escalation will depend on the toxicity profile observed at these dose levels, and reevaluation of the regimen by the study team may be done.
- 16.226 If a patient fails to complete the first 2 cycles of therapy (one cycle of lenalidomide and one cycle of lenalidomide in combination with AT-101) for reasons other than dose-limiting toxicity defined adverse events, the patient will be regarded as uninformative in regard to the primary study goal and an additional patient will be treated at the current dose level; however, all toxicity information will be utilized in the analysis.

16.227 Operating Characteristics for standard cohort of 3 design: The following table gives the probability of dose escalation at a single dose level as a function of the true probability of DLT at that level using the cohorts of 3 design described above.

| True Rate of DLT (%) | Probability of Dose Escalation |
|-------------------------|--------------------------------|
| 10 | 0.91 |
| 20 | 0.71 |
| 30 | 0.49 |
| 40 | 0.31 |
| 50 | 0.17 |

16.23 Analysis Plans: All the relevant results pertaining to toxicity, MTD, response, timed endpoints and laboratory correlates will be examined in an exploratory and hypothesis-generating fashion. The small sample size and the heterogeneous patient population associated with phase I studies restricts the generalizability of the results. Any notable statistical result should only be viewed as preliminary evidence for further study in Phase II trials rather than a definitive finding in and of itself.

16.231 Adverse Events Profile

Platelets and hemoglobin will be graded according to the Grading Scale for Hematologic Adverse Events in CLL Studies in Appendix V. The number and severity of all adverse events (overall and by dose-level) will be tabulated and summarized in this patient population. The Grade 3+ adverse events will also be described and summarized in a similar fashion. This will provide an indication of the level of tolerance for this treatment combination in this patient group.

16.232 Toxicity Profile

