The term toxicity is defined as adverse events that are classified as either possibly, probably, or definitely related to study treatment. Platelets and hemoglobin will be graded according to the Grading Scale for Hematologic Adverse Events in CLL Studies in Appendix V. All other toxicities will be evaluated via the ordinal CTC standard toxicity grading.

Overall toxicity incidence as well as toxicity profiles by dose level, patient and tumor site will be explored and summarized. Frequency distributions, graphical techniques and other descriptive measures will form the basis of these analyses.

16.233 Response Profile

A response is defined to be a CR, CRi, CCR, nPR, or PR noted as the objective status. Response will be evaluated using all cycles of treatment. All patients meeting the eligibility criteria who have signed a consent form and have begun treatment will be evaluable for response.

Responses will be summarized by simple descriptive summary statistics delineating complete and partial responses as well as stable and progressive disease in this patient population. The number of responses may indicate further evaluation for specific disease types in a Phase II setting.

- 16.3 **Phase 2 Statistical Design**: This is a Phase II study designed to assess the overall response rate as well as the toxicity associated with lenalidomide in combination with AT-101 in patients with relapsed CLL.
 - 16.31 Decision Rule:

In a study of 44 patients, single agent Lenalidomide was given at a starting dose of 10 mg daily and could be escalated or de-escalated based on tolerability and response (Ferrajoli et al, 2008).⁶⁰ The overall response rate for all patients was 32%, where the median dose was 10 mg.

| Lenalidomide dose | Response rate |
|-------------------|---------------|
| 5 mg | 3/11 (27%) |
| 10 mg | 4/16 (25%) |
| 15 mg | 4/12 (33%) |
| 20 mg | 1/2 (50%) |
| 25 mg | 2/3 (67%) |

With the addition of AT-101, an overall response rate of 50% would be of interest.

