 - 16.422 Time to Progression: Time to disease progression is defined as the time from registration to the earliest date of documentation of disease progression. If a patient dies without a documentation of disease progression the patient will be considered to have had tumor progression at the time of their death unless there is sufficient documented evidence to conclude no progression occurred prior to death. In the case of a patient starting treatment and then never returning for any evaluations, the patient will be censored for progression on day 1 post-registration. Patients who receive subsequent treatment for CLL before disease progression will be censored on the date of their last disease assessment prior to initiation of the subsequent treatment. The distribution of time to progression will be estimated using the method of Kaplan-Meier (Kaplan-Meier, 1958).⁶³
 - 16.423 Adverse Events: Platelets and hemoglobin will be graded according to the Grading Scale for Hematologic Adverse Events in CLL Studies in Appendix V. The maximum grade for each type of adverse event, regardless of causality, will be recorded and reported for each patient, and frequency tables will be reviewed to determine adverse event patterns. Adverse events will continue to be recorded and reported up to 30 days after the last day of study drug treatment.
- 16.43 Correlative Analyses: Due to the small overall sample size, the results of the following analyses will be considered exploratory and hypothesis-generating in nature.
 - 16.431 Immune cellular microenvironment: To determine the effect of lenalidomide on the immune effector arm, immune function will be evaluated before and during treatment by assessing T and NK cell quantification in both peripheral blood and bone marrow. Changes in these values over time will be both graphically and quantitatively summarized and explored. In addition, these values will be explored in

relation to response (responder vs non-responder as well as by quality of response, i.e. CR vs PR).

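### The adverse event tables promised in 16.231, 16.232 and 16.423 go beyond the data that 10.6 and 10.61 require, so low-grade rows may be under-counted and grade 2 rows mislabelled

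*Combined protocol and SAP*

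**What the plan says.** **Analysis side (Section 16).** In phase I, 16.231 states: "The number and severity of all adverse events (overall and by dose-level) will be tabulated and summarized in this patient population". It then asks for a further summary of grade 3 and higher events. Section 16.232 covers related events: "The term toxicity is defined as adverse events that are classified as either possibly, probably, or definitely related to study treatment". It plans an overall incidence as well as profiles by dose level. In phase II, 16.423 states: "The maximum grade for each type of adverse event, regardless of causality, will be recorded and reported for each patient".

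**Collection side (Section 10).** Section 10.6 introduces a short table: "Adverse events to be graded at each evaluation and pretreatment symptoms/conditions to be evaluated at baseline per the CTCAE v4.0 grading". The table has four terms: platelet count decreased, anemia, constipation and ileus. For everything else, 10.61 requires submission of "the following AEs experienced by a patient and not specified in Section 10.6", and lists three classes:

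- grade 2, if at least possibly related (10.611);
- "Grade 3 and 4 AEs regardless of attribution to the study treatment or procedure" (10.612);
- grade 5: deaths within 30 days of the last treatment or procedure, and later deaths if at least possibly related (10.613).

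Grade 1 is not on the list. Nor is grade 2 judged unlikely or unrelated.

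**The concern.** The analysis sections set no grade floor, and two of them set no attribution filter. The collection sections set both for all but four terms. Nothing in the plan limits the tables to the classes that must be submitted.

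The low grades are where AT-101 events are expected. Section 15.27 says of this drug: "Most adverse events have been of low grade". It names nausea, vomiting, anorexia, dehydration, hypokalemia and fatigue as frequent, and none of these six is in the 10.6 table. Safety is a secondary goal (2.23), and the toxicity profile is part of the phase I aim (16.1, 16.2). A reader of a table headed regardless of causality could take sparse grade 1 and grade 2 rows as good tolerability, when part of the sparseness comes from the submission rule.

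**Working it through.** **Step 1. Collection and analysis side by side.**

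| Event class | Required by 10.6 / 10.61? | In the 16.231 and 16.423 tables? | In 16.232 (related only)? |
|---|---|---|---|
| Four 10.6 terms, any grade | Yes | Yes | Yes, if related |
| Other term, grade 1, related | No | Yes | Yes |
| Other term, grade 1, unlikely or unrelated | No | Yes | No |
| Other term, grade 2, at least possibly related | Yes | Yes | Yes |
| Other term, grade 2, unlikely or unrelated | No | Yes | No |
| Other term, grade 3-4, any attribution | Yes | Yes | Yes, if related |
| Grade 5, within 30 days of last treatment | Yes | Yes | Yes, if related |

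The mismatch lies in the three rows marked No under collection. There is one exception. Under 10.4, a serious grade 1 or 2 event with hospitalization of at least 24 hours needs an expedited report, whether or not it is thought related. Section 10.11 sends every expedited event to routine reporting as well, so these events do reach the data.

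**Step 2. Is the all-event table shorthand for grade 3 and higher?** No. Section 16.231 asks for the grade 3 and higher summary in addition, so the all-event table is a separate product. In 16.423 the maximum grade is to be recorded as well as reported, which is a statement about data and not only about layout.

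**Step 3. Section 8.3.** The AT-101 table there is triggered by nausea of grade 2 or higher, vomiting of grade 2 or higher, and abdominal pain of any grade, when they last more than 48 hours. Related grade 2 events and all grade 3-4 events are already required. Left out are grade 1 abdominal pain and grade 2 events judged unlikely or unrelated.

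**Step 4. The one stated figure that depends on capture.** Section 16.21 says that 6 patients at the MTD give at least 82% probability of observing a toxicity with 25% incidence. Check: 1 - (1 - 0.25)^6 = 1 - 0.75^6 = 0.822. The figure reproduces, on the premise that every occurrence is captured.

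Let c be the share of affected patients whose worst related grade falls in a class that must be submitted. The probability becomes 1 - (1 - 0.25c)^6, and the expected number tabulated among 37 patients is 37 x 0.25 x c. The documents do not give c, so the values below are assumptions for an unsolicited term.

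| c (assumed) | Probability of appearing in 6 patients | Expected number tabulated of 37 |
|---|---|---|
| 1.00 | 0.822 | 9.25 |
| 0.90 | 0.783 | 8.33 |
| 0.75 | 0.712 | 6.94 |
| 0.50 | 0.551 | 4.63 |
| 0.25 | 0.321 | 2.31 |

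**Step 5. What is not touched.** Non-hematologic dose-limiting toxicities (7.221) start at grade 3, and every DLT goes directly to the Study Chair (7.213). The grade 3 and higher summary uses classes that are required. The stopping rule in 16.52 uses related non-hematologic events of grade 4 or higher, which are required. The response endpoint uses no adverse event data, so sample size, significance level and power stay as stated.

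**The case against.** The best defence is that 10.61 sets a minimum. It says what must be submitted and does not forbid more. The forms are not in the documents, adverse events are assessed before each of cycles 2-12, at discontinuation and in observation (4.0), and a Nadir/Adverse Event Form is due at each evaluation (18.1). Section 16.423 can also be read as a summary of whatever was submitted. Which low-grade terms to solicit is a design choice, and the plan already solicits ileus and constipation. No trial decision rests on the low-grade rows.

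Much of this stands. It limits the claim to events that are not required and so may be under-counted. It does not remove the conflict: sites that follow 10.61 exactly would not supply what 16.231 and 16.423 describe, and voluntary extra entries would make the low-grade rows uneven between patients.

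Three stronger readings are tempting, and the documents do not support them.

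- A reader might infer that every low-grade event outside the four terms will be absent, or will appear as zero. The hospitalization route in 10.4 and 10.11 contradicts this, and the forms may accept more than 10.61 demands.
- A reader might size the gap from the daily-dose AT-101 cohort in Section 1.0, where 11 of 12 patients had grade 1-2 gastrointestinal toxicity. That is a different schedule. The pulse cohort, which is closer to this trial, had 2 of 6. Neither figure separates grade 1 from grade 2, and related grade 2 events are collected here.
- A reader might infer that the 8.3 triggers go largely unrecorded. Step 3 shows that most are required whenever they are judged related.

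**Conclusion.** The point holds as an inconsistency between the collection rules and the analysis text, and it is minor. For terms outside the 10.6 table, grade 1 and any-grade rows may be too low, and grade 2 rows would be largely related events under a label that says otherwise. The related-toxicity incidence in 16.232 is affected through related grade 1 events. The four 10.6 terms are complete at all grades, and other terms are complete at grades 3-4.

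The size cannot be derived from the documents. The fall from 0.82 to between 0.78 and 0.32 in Step 4 rests wholly on assumed capture shares of 0.9 to 0.25. It shows how the 82% statement depends on capture and is not an estimate for this trial. The conclusion assumes that sites submit what 10.61 requires and little more.

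**What to change.** Restate 16.231, 16.232 and 16.423 to match collection: all grades for the terms in 10.6, grade 2 events at least possibly related, and grade 3 and above regardless of attribution. Within 16.232, that means related events at all grades for the 10.6 terms and at grade 2 and above for the rest. Carry the same limits into the table titles and footnotes, and note that hospitalized serious grade 1-2 events enter through expedited reporting. Add to the 16.21 detection statement that, for unsolicited terms, it refers to toxicities that reach a submitted grade. This costs wording only.

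As a cheap addition, put nausea, vomiting, abdominal pain and fatigue in the 10.6 table. The main expected low-grade AT-101 toxicities, and the any-grade abdominal pain named in 8.3, would then be captured at scheduled evaluations. The downside is four more terms to grade per visit, at assessments that already take place; the change to the form itself cannot be costed because the form is not in the documents. Anorexia, dehydration and hypokalemia would stay under the 10.61 rule and be covered by the restated labels. No dose, treatment rule, sample size or error rate changes.

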16.5 Data & Safety Monitoring

- 16.51 The principle investigator(s) and the study statistician will review the study at least twice a year to identify accrual, adverse event, and any endpoint problems that might be developing. The Mayo Clinic Cancer Center (MCCC) Data Safety Monitoring Board (DSMB) is responsible for reviewing accrual and safety data for this trial at least twice_a year, based on reports provided by the MCCC Statistical Office.
- 16.52 Adverse Event Stopping Rule for phase II patients: The stopping rule specified below is based on the knowledge available at study development. We note that the rule may be adjusted in the event of either (1) the study re-opening to accrual or (2) at any time during the conduct of the trial and in consideration of newly acquired information regarding the adverse event profile of the treatments under investigation. The study team may choose to suspend accrual because of unexpected adverse event profiles that have not crossed the specified rule below.

Accrual will be temporarily suspended to this study if at any time we observe events considered at least possibly related to study treatment (i.e. an adverse event with attribute specified as "possible," "probable," or "definite") that satisfy either of the following:

- if 5 or more patients in the first 14 treated patients experience a grade 4 or higher non-hematologic adverse event at least possibly related to treatment.
- if after the first 14 patients have been treated, 30% of all patients experience a grade 4 or higher non-hematologic adverse event at least possibly related to treatment.

We note that we will review grade 4 and 5 adverse events deemed "unrelated" or "unlikely to be related", to verify their attribution and to monitor the emergence of a previously unrecognized treatment-related adverse events

